The difference between ManCRR and AirRR is comparing with the difference between CapRR and ManCRR to indicate the bias of Airmod are non-inferior to the reference devices at the margin of 3 bpm, which also demonstrates substantial equivalence.

4.2 The difference of ManCRR minus AirRR and ManCRR minus CapRR indicates non-inferiority at margin of 2 bpm (M2) and sampling rate 1Hz.

To evaluate whether Airmod can approach a strict standard suggested by clinicians, the difference between ManCRR and AirRR is comparing with the difference between CapRR and ManCRR to indicate the bias of Airmod are non-inferior to the reference devices at the margin of 2 bpm, which indicates the largest clinically acceptable difference.

According to 7.2, part of the measurement result within subject will be censored and excluded in the paired non-inferiority test. The principle of exclusion is based on the investigator reported failure event/period of Airmod or Capnostream™35, the report will be confirmed by the principal investigator. The data prior to discontinuation or following a fixed machine failure period will be included in the paired non-inferiority test.

5. The usability questionnaire as reference [Usability_Airmod] and descriptive analysis will be performed and recorded.

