4.4 Endpoints

Primary Endpoint:

The difference between AirRR and ManCRR, which is greater than -3 establishes non-inferiority. The unit in this calculation is bpm and sampling rate is 1 Hz.

Secondary Endpoints:

1. The accuracy of inhalation classification in the segmentation basis is greater than 82.5% at the 95% Cl. The performance metrics (F1-socre, MAPE) at event level will be demonstrated and target for F1-score > 0.8, MAPE < 0.5.

2. To measure the agreement of AirRR and ManCRR on concordance correlation coefficient, and on their mean and bias by Bland-Altman analysis.

3. Use paired t-test to compare the response time of Airmod versus Capnography on Capnostream[™]35 after administration of jaw thrust. In the target of p<0.05 indicates significance.

4.1. The difference of ManCRR minus AirRR and ManCRR minus CapRR indicates non-inferiority at margin of 3 bpm (M1) and sampling rate 1Hz.

4.2. The difference of ManCRR minus AirRR and ManCRR minus CapRR indicates non-inferiority at margin of 2 bpm (M2) and sampling rate 1Hz.

5. The absence of unanticipated serious adverse device effect (USADE) during study period and the questionnaire.

Evaluating the Non-Inferiority of Airmod to Capnostream™35 on Respiratory Rate Monitoring and User Experience Clinical Evaluation

[Time Frame:

Non-Anesthesia Stage: Up to 40 patients will be randomly assigned to non-anesthesia stage assessment, the measurement will be evaluated after enrollment with ICF, at the non-operating room (NOR) area. (5~30 minutes)

Procedure Stage: From firstly anesthetic administration to end of procedure. (Depends on procedure 10mins ~ few hours)

Transportation Stage: During transportation of subjects. (1~10 minutes)

Post anesthesia care unit stage : From subjects arrive post anesthesia care unit (PACU) to discharge from PACU (PAR or PADSS score \geq 9) (At least 15 minutes)]

5 Study Methods

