the actual measurement of the respiratory event.

9.2.2 Analysis to measure the agreement between AirRR and ManCRR.

Bland Altman analysis, and concordance correlation is adopted to measure the agreement between AirRR and ManCRR. The quantitative results of respiratory rate from these devices under test over time are evaluated by the above mentioned method to analyze the mean and bias from the plot and concordance correlation coefficient.

Fig 9. Bland Altman between AirRR and ManCRR (Example)

Fig 10. Correlation between AirRR and ManCRR (Example)

Fig 11. Correlation between AirRR and ManCRR during induction period (Example)

Evaluating the Non-Inferiority of Airmod to Capnostream™35 on Respiratory Rate Monitoring and User Experience Clinical Evaluation

Fig 12. Correlation between AirRR and ManCRR during Inter-operation period (Example)

Fig 13. Correlation between AirRR and ManCRR during transportation and PACU period (Example)

Also, we apply a sensitivity test for Airmod by comparing the reference method at each time point and calculating the absolute deviations in breaths per minute (bpm). As a measure of accuracy, absolute deviations were calculated as a percent of reference.

Percent absolute deviation were averaged for each subject yielding overall measures of accuracy. To evaluate the accuracy of Airmod, the individual percent absolute deviation was compared for each monitoring time point by subtracting ManCRR from AirRR and then averaged within subject. A paired t test was used to evaluate significance across subjects.

To measure the precision of Airmod for each subject, the standard deviation of percent deviations (in nonabsolute value) was calculated. The precision of Airmod was compared through a paired t test of the subject-specific standard deviations of Airmod's percent deviations from reference.

9.2.3 Analysis to evaluate the response time of the first breath detection followed by administration of jaw thrust during the apnea period. The 3rd secondary objective is to compare the response time of Airmod versus Capnography.

Use paired t-test to compare the response time of Airmod versus Capnography on Capnostream[™]35 after administration of jaw thrust. The target of p<0.05 indicates significance difference.

Evaluating the Non-Inferiority of Airmod to Capnostream™35 on Respiratory Rate Monitoring and User Experience Clinical Evaluation

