Fig 14. Breath detection (Capnostream[™]35 & Airmod) followed by administration of jaw thrust during the apnea period

9.2.4 Analysis to compare the influence of subjects to variated breath rates on respiratory rate monitoring in bpm as measured by Airmod, manual-scored and Capnostream[™]35.

In order to determine the performance of Airmod and Medtronic Capnostream[™]35 in the ITT population, we compare them with the gold standard (ManCRR). The difference of ManCRR to AirRR and ManCRR to CapRR are parallel listed and compared to indicates non-inferiority at margin of 3 bpm (M1). The range of respiratory rate are also reported as 95% Confidence Interval of measurement. We proposed to further challenge the largest clinical acceptable range. The difference of ManCRR minus AirRR and ManCRR minus CapRR indicates non-inferiority at margin of 2 bpm (M2) are proposed to be the target of efficacy analysis.

9.2.5 Analysis to evaluate the usability of Airmod.

The demography of users will be shown in pie charts in proportion. (Recorded in [CRF_appendix 9_ Questionnaire POC] Part 1)

The evaluation of usability will be calculated from the Part 2 of [CRF_appendix 9_ Questionnaire POC], the pass rate greater than 90% showed that Airmod is good to manipulate.

10 Safety Analyses

All candidates who were subjected to the device with Airmod and CapnostreamTM35 will be included in the safety analyses (performed in the Safety population) and data will be summarized using descriptive statistics. By reporting the numbers of adverse events (AE)/serious adverse events(SAE) within the trial to indicate the incidence rate of safety issues. We will also present the total number of patients suffering from AE/SAE and its percentage of all populations.

The incidence of adverse events will be tabulated, summarized by intensity and relationship to the investigational product (IP).

• All-Cause Mortality: A table of all anticipated and unanticipated deaths due to any cause, with number and frequency of such events in each arm/group of the clinical study.

Evaluating the Non-Inferiority of Airmod to Capnostream™35 on Respiratory Rate Monitoring and User Experience Clinical Evaluation

- SAEs: A table of all anticipated and unanticipated SAEs, grouped by organ system, with number and frequency of such events in each arm/group of the clinical study. (See AEs definition below).

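### Secondary endpoint 4 compares signed differences, so it addresses mean bias at most and cannot show that Airmod's rate error is no worse than Capnostream 35's

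*SAP*

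**What the plan says.** SAP 4.4 defines secondary endpoints 4.1 and 4.2 through ManCRR minus AirRR and ManCRR minus CapRR, at 3 bpm (M1) and 2 bpm (M2). SAP 9.2.4 calls ManCRR the gold standard for both devices and states: "The difference of ManCRR to AirRR and ManCRR to CapRR are parallel listed and compared to indicates non-inferiority". It repeats the subtraction for the stricter margin: "The difference of ManCRR minus AirRR and ManCRR minus CapRR indicates non-inferiority at margin of 2 bpm (M2"). It gives no hypothesis, formula, test statistic or sidedness, and no absolute or squared error.

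Protocol 9.4.3 (items 4.1 and 4.2) describes the same comparison with the second difference in the opposite order: "The difference between ManCRR and AirRR is comparing with the difference between CapRR and ManCRR to indicate the bias of Airmod are non-inferior". It adds that meeting the 3 bpm margin also demonstrates substantial equivalence.

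Absolute deviations of AirRR from the capnographic reference appear in the sensitivity test of SAP 9.2.2. For accuracy it says "A paired t test was used to evaluate significance across subjects". For precision it applies another paired t test, to the subject-specific SDs of Airmod's percent deviations. Neither test names a CapRR quantity.

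**The concern.** The stated objective is to show that Airmod's accuracy and performance are non-inferior to Capnostream 35. That requires comparing how far each device lies from the reference. A mean of signed differences does not measure distance, because over-counts and under-counts offset each other. The primary endpoint is also a signed mean, and it compares AirRR with ManCRR only, so it does not fill the gap.

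Two wrong conclusions are possible. A device with large errors in both directions could be declared non-inferior. A device closer to the reference than Capnostream could fail because Capnostream itself is biased.

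**Working it through.** The documents give no effect size, power or error SD for endpoint 4, so there is no planned figure to reproduce. The check is algebra, followed by illustrations whose error sizes are assumptions.

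**Inputs from the documents:** 300 subjects (SAP 7.1); margins 3 and 2 bpm (SAP 4.4); final one-sided nominal level 0.02450 and boundary z = 1.9686 (SAP 9.1.1), equivalent to a 95.1% interval since 1 - 2 × 0.0245 = 0.951; pilot SD 3.29647 (SAP 9.1, table of pilot-study inputs).

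**Assumed:** 40 one-minute values per subject, errors independent between minutes, Capnostream error normal with mean 0 and SD 1 bpm.

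**1. Three readings of the comparison**
- *Paired, common time points:* (ManCRR - AirRR) - (ManCRR - CapRR) = CapRR - AirRR. ManCRR drops out. SAP 8.2.5 supports this reading: it forms each device's difference from ManCRR and then subtracts one from the other.
- *Each difference tested separately against the margin:* ManCRR stays. Opposite errors still average out, and the devices are not formally compared.
- *Protocol 9.4.3 order taken literally:* (ManCRR - AirRR) - (CapRR - ManCRR) = 2·ManCRR - AirRR - CapRR. ManCRR stays, but this adds the two biases instead of comparing them. If both devices under-read by 4 bpm it equals 8, although they are equally accurate.

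**2. Airmod wrong by +6 or -6 bpm with equal probability**
- Expected signed contrast: 0.
- Standard error: √((36 + 1)/(300 × 40)) = √(37/12,000) = 0.056. Half-width: 1.9686 × 0.0555 = 0.11 bpm. Both margins are met easily.
- Mean absolute error: Airmod 6; Capnostream √(2/π) × 1 = 0.80. Excess: 6 - 0.80 = 5.2 bpm.

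**3. Airmod error normal, mean 0, SD 3.29647**
- This assumes that the pilot SD is the SD of AirRR - ManCRR; the SAP does not say so.
- Mean absolute error: 3.29647 × 0.798 = 2.63. Excess: 2.63 - 0.80 = 1.83 bpm.
- Variance of the absolute-error contrast: (3.29647² + 1)(1 - 2/π) = 4.31. The upper limit is 1.83 + 1.9686 × √(4.31/12,000) = 1.87 if minutes are independent. If instead the errors were constant within each subject, it is 1.83 + 1.9686 × √(4.31/300) = 2.07.
- So M1 is met and M2 is borderline on the absolute-error scale, while the signed contrast is still 0 in expectation.

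**4. Other error patterns** (simulation: 300 subjects, 30 one-minute values each, 200 replicates, z = 1.9686, all error sizes assumed; values in bpm)

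| Scenario | Signed contrast CapRR - AirRR (interval) | Absolute-error contrast (upper limit) |
|---|---|---|
| Airmod unbiased, SD 8; Capnostream SD 1 | -0.01 (-0.18 to 0.16) | 5.58 (5.68) |
| Airmod subject-level bias, SD 6 | -0.02 (-0.70 to 0.66) | 4.05 (4.45) |
| Airmod near-exact; Capnostream over-reads by 4 | 4.00 (3.99 to 4.02) | -3.60 (-3.59) |
| Airmod over-reads by 4; Capnostream accurate | -4.00 (-4.03 to -3.97) | 3.20 (3.23) |
| Both under-read by 4 | 0.00 (-0.03 to 0.03) | 0.00 (0.03) |

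The first two rows pass both signed margins in every replicate, although Airmod is much less accurate. The third fails both although Airmod is much more accurate. The fourth passes a one-sided upper bound and fails a two-sided one, so the unstated sidedness matters.

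**5. SAP 9.2.2 paired t tests**
With no comparator, the literal test is of a non-negative quantity against zero. For an assumed mean absolute deviation of 8% and SD of 5% in 300 subjects, t = 0.08/(0.05/√300) = 27.7. Any imperfect device would be rejected.

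**The case against.** **The endpoint is about bias.** Protocol 9.4.3 uses that word, and bias is properly signed. This stands as a reason to keep the signed analysis. It does not support the same section's step from bias to substantial equivalence, or an objective framed as accuracy.

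**A reader might infer that ManCRR always cancels.** The documents do not support that. No contrast is written out, cancellation is one of three readings, and it is exact only at common time points. The conclusion does not depend on it, because the other two readings do not compare accuracy either.

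**A reader might infer that nothing else in the plan resists cancelling errors.** That is also too strong.
- MAPE has a target below 0.5, and the protocol chose it so that opposite errors do not cancel. It is measured against ManARR in capnography's less sensitive periods, without CapRR, and the SAP 8.2.4 formula omits the absolute value.
- Bland-Altman limits and the concordance coefficient (SAP 8.2.5, 8.2.6 and 9.2.2) would expose a noisy device. An error of +6 or -6 bpm would give limits near 1.96 × 6 = 11.8 bpm either side. But no numeric limit or concordance target is set. The protocol's rule, that differences lie within their own 95% limits, is largely met by construction. Neither analysis has a device-versus-device criterion.

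**The error sizes are invented.** True. At the pilot SD the excess is about 1.8 bpm, which meets M1 and may meet M2. The illustrations show what the endpoint cannot detect; they do not predict Airmod's performance.

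**SAP 9.2.2 does name a pair, AirRR and ManCRR.** It subtracts one from the other to form the deviation, but the quantity then tested is that deviation alone. It is a sensitivity test with no success criterion, so this part is secondary.

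**Conclusion.** The point holds in this form. As written, endpoint 4 addresses mean bias at most and cannot establish that Airmod's error against ManCRR is no worse than Capnostream's. That follows from the signed definitions and needs no numerical assumption.

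The size does rest on assumptions: an excess mean absolute error of about 5.2 bpm goes undetected with random errors of 6 bpm, and about 1.8 bpm with an error SD of 3.3 bpm, against a Capnostream SD of 1 bpm. The converse failure, rejecting the more accurate device, needs a Capnostream bias larger than the margin (4 bpm in the illustration), and the documents give no such figure.

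The documents do not support a conclusion that Airmod is inaccurate, or that a poor device would pass unnoticed through all planned output. The gap is the lack of a formal accuracy comparison with Capnostream's displayed rate, and it should be closed. The absence of a comparator in the SAP 9.2.2 t tests is a separate, smaller defect.

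**What to change.** 1. Keep the signed difference in SAP 9.2.4 as the bias analysis. Write out the contrast, hypotheses and sidedness, and use the same order of subtraction in Protocol 9.4.3.
2. Add an accuracy contrast. For each subject, take the mean over common minutes of |AirRR - ManCRR| - |CapRR - ManCRR|. Compare the upper confidence limit of the mean across subjects, at the final nominal level (95.1% interval), with M1 and then M2.
3. State why 3 and 2 bpm are acceptable as differences in mean absolute error. The plan applies them to bias, and they do not carry over automatically.
4. Base the accuracy and substantial-equivalence claim on the new contrast.
5. In SAP 9.2.2, pair each subject's Airmod percent absolute deviation, and the SD of its percent deviations, with the same quantities for CapRR.

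The cost is revised wording in SAP 9.2.2 and 9.2.4 and Protocol 9.4.3, a short margin justification, and a criterion that is somewhat harder to meet. AirRR, CapRR and ManCRR are already planned for every subject, so no new data are needed.

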10.1 Adverse Events

The following list describes the common adverse events of procedural sedation (Non-ADE) and the device-related adverse event (ADE) to be recorded in this study.

| Patient Problems | ADE | non- ADE | Definition | |
|------------------------------|-----|-------------|--|---|
| Hypotension | - | AE | Decline for more than 30% from the Baseline over 1minutes | * |
| Bradycardia | - | AE | HR < 50 BPM | * |
| Tachycardia | - | AE | HR > 120 BPM | * |
| Hypoxemia | - | AE | Hypoxemia < 85 mmHg | 0 |
| Minor oxygen desaturation | - | - | SPO ₂ < 94 Not reported | |
| Moderate oxygen desaturation | - | AE | SPO ₂ < 90 | * |
| Severe oxygen desaturation | - | AE | SPO ₂ < 80 | * |
| Hypertension | - | AE | Reach 30% over the baseline for more than 1mintutes | * |
| Apnea(not prolonged) | - | - | Apnea 15-30 second | * |
| Apnea(long) | - | AE | Apnea > 30 second | * |
| AW obstruction | - | AE | | |
| Seizure | - | AE | | * |
| Failed sedation | - | - | | |
| Allergy | - | AE | | |
| Cardiovasular collapse | - | SAE | | |

Evaluating the Non-Inferiority of Airmod to Capnostream[™]35 on Respiratory Rate Monitoring and User Experience Clinical Evaluation

| Cardiac arrest | - | SAE | | |
|---|-----|-----|--|------------------|
| Myocardial infarction | - | SAE | | |
| Aspiration Pneumonia | - | SAE | | \bigtriangleup |
| Prolonged Cognitive Dysfunction (> 6month) | - | SAE | | \bigtriangleup |
| Encephalopathy | - | SAE | | \bigtriangleup |
| Skin irritated allergic dermatitis | AE | - | | |
| Skin irritation related allergenic shock | SAE | | | |
| | | | Red color is indicating "report to the IRB in a timely fashion". | |
| REF: https://www.ncbi.nlm.nih.gov/pmc/articles/PMC5836671/ | | | * Not include Transient Event (< 1mins) | |
| REF: https://pubmed.ncbi.nlm.nih.gov/27126387/ | | | riangle could lead to elongation hospital stay | |
| | | | O Hard to measurement | |

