9.4.4 SAFETY ANALYSES

All candidates who were subjected to the device with Airmod and Capnostream™35 will be included in the safety analyses (performed in the Safety population) and data will be summarized using descriptive statistics. By reporting the numbers of adverse events (AE)/severe adverse events(SAE) within the trial to indicate the incidence rate of safety issues. We will also present the total number of patients suffering from AE/SAE and its percentage of all population.

The incidence of adverse events will be tabulated, summarized by intensity and relationship to the investigational product.

Details refer to the SAP.

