7.5.3 Stopping Rule

We're proposing not to apply the stopping rule for efficacy analysis in this study. Therefore, a failure end point in the interim analysis will not prohibit the following study. However, by the charter of DSMB. They are obligated to monitor, and terminate the study on a serious protocol deviation, or server medical device related adverse events reported.

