- Other (Not Including Serious) AEs: A table of anticipated and unanticipated events (not included in the SAEs table) within any subsets of the clinical study, grouped by organ system, with number and frequency of such events in each arm/group of the clinical study.
- ADEs: this category indicates the anticipated device-related adverse events which may be related to the digital stethoscope AS-101.

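### The SAP adverse event table labels events as device-related by type and confines device effects to anticipated stethoscope reactions, so harm linked to a wrong or missing Airmod reading may be missed

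*SAP*

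**What the plan says.** Five places bear on this point.

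- **SAP 10.1, adverse event table.** The lead-in reads "The following list describes the common adverse events of procedural sedation (Non-ADE) and the device-related adverse event (ADE) to be recorded in this study". Each row then has an entry or a dash under ADE and under non-ADE. The two ADE entries are "Skin irritated allergic dermatitis | AE" and "Skin irritation related allergenic shock | SAE". Long apnea, moderate and severe desaturation, airway obstruction and cardiac arrest all have a dash under ADE and an entry under non-ADE.
- **SAP section 10, ADE bullet.** "ADEs: this category indicates the anticipated device-related adverse events which may be related to the digital stethoscope AS-101". Airmod is not named. Protocol 6.1.1 identifies Airmod as the investigational product and AS-101 as a stethoscope already marketed in Taiwan.
- **Protocol 9.4.4, repeated in SAP section 10.** Adverse events are to be tabulated and "summarized by intensity and relationship to the investigational product".
- **SAP 4.4, secondary endpoint 5.** "The absence of unanticipated serious adverse device effect (USADE) during study period and the questionnaire".
- **SAP 7.5.3.** The DSMB, acting under its charter, is to "terminate the study on a serious protocol deviation, or server medical device related adverse events reported".

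Three other statements matter. Under Protocol 8.2 the investigator evaluates adverse events throughout the study. SAP section 10 tabulates both anticipated and unanticipated SAEs. Protocol 10.2.6 says adverse events are recorded so that device-related hazards can be analysed.

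**The concern.** A summary by relationship to the investigational product needs a judgement on each event. A table that sorts event types into ADE and non-ADE beforehand gives that answer before the event happens. The two approaches can disagree, and the documents do not say which prevails.

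The disagreement matters most for the harm specific to a respiratory rate monitor. A skin reaction comes from the sensor and tape. A false or absent rate comes from the software under study, and its clinical consequence would appear as apnea, desaturation, airway obstruction or arrest. Those are rows marked non-ADE.

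The design gives little else to fall back on. Under SAP 7.2 both devices are placed on every enrolled patient, and Protocol 6.3 says the study is neither randomized nor blinded. With no device-free group, event rates cannot reveal a device effect, so the safety conclusion leans on case-by-case causality. If the row label stands in for that judgement, a finding of no USADE could partly reflect how events were labelled.

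**Working it through.** The documents give no figure for this endpoint to reproduce. The check is a row count followed by a comparison of the passages.

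**1. Row count of the SAP 10.1 table**

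| Column entry | Rows | Count |
|---|---|---|
| Non-ADE, AE | hypotension, bradycardia, tachycardia, hypoxemia, moderate desaturation, severe desaturation, hypertension, long apnea, airway obstruction, seizure, allergy | 11 |
| Non-ADE, SAE | cardiovascular collapse, cardiac arrest, myocardial infarction, aspiration pneumonia, prolonged cognitive dysfunction, encephalopathy | 6 |
| Neither column | minor desaturation, apnea of 15 to 30 seconds, failed sedation | 3 |
| ADE, AE | skin dermatitis | 1 |
| ADE, SAE | skin-related allergic shock | 1 |

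Total: 11 + 6 + 3 + 1 + 1 = 22. Non-ADE: 11 + 6 = 17 of 22. ADE: 1 + 1 = 2 of 22. SAE rows: 6 + 1 = 7, of which 6 are non-ADE.

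The seven rows on oxygenation, apnea and airway obstruction are hypoxemia, three grades of desaturation, two lengths of apnea, and airway obstruction. Five are non-ADE, two are in neither column, and none is ADE.

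**2. Table against the ADE bullet.** The bullet limits the category in two ways: to anticipated events and to AS-101. Both ADE rows fit it. An Airmod-related event falls outside it on the second limit, and an unanticipated event on the first. The stated ADE category therefore has no place for an unanticipated effect of Airmod, although endpoint 5 concerns unanticipated device effects.

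**3. Table and bullet against the relationship summary.** Protocol 9.4.4 and SAP section 10 ask for relationship to the investigational product, which is Airmod. The table and bullet speak only of relationship to the stethoscope, and by event type. These are different questions, and the answers can differ for the same event.

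**4. Is there a rule that settles the conflict?** Protocol 8.2 provides for investigator evaluation but gives no causality scale or criteria. USADE is spelled out as an abbreviation and not defined operationally. The SAE bullet in SAP section 10 sends the reader to the AE definitions that follow, which leads to this same table. No passage says that a judgement on the individual event overrides the row.

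**5. Example.** Suppose Airmod shows a normal rate during an apnea and the patient then has a cardiac arrest. The table row gives non-ADE, SAE. A relationship-to-Airmod assessment could give related. The documents do not say which of the two feeds endpoint 5 or is reported to the DSMB as device-related.

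**The case against.** The strongest reply is that the table is only a reference list of common sedation events, with relationship judged elsewhere. Protocol 9.4.4 and SAP section 10 commit to a relationship summary, Protocol 8.2 has the investigator evaluate events, SAP section 10 tabulates unanticipated SAEs, and Protocol 10.2.6 foresees a device-hazard analysis. Capnostream 35, with its CO2 and SpO2 readings, runs at the same time, which may reduce reliance on Airmod. The AE form and site instructions are not among the documents, so how a site would record a given event is not known.

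Much of this stands, and it rules out several stronger readings:

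- A reader might infer that harm from an Airmod misreading cannot count toward endpoint 5. The documents do not support that. The endpoint does not refer to the ADE column, and a USADE is unanticipated by name, so a list of common events and anticipated ADEs does not bound it.
- A reader might infer that such harm cannot reach the DSMB. SAP 7.5.3 speaks of device-related events reported and defers to a charter that was not supplied; it does not cite the table.
- A reader might count every dash under ADE and conclude that 20 of 22 rows are assigned as not device-related. Three of those rows have a dash in both columns, so the number assigned non-ADE is 17.

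The reply does not remove the conflict. The commitments it relies on supply no causality criteria and no rule of precedence, and the ADE bullet still leaves out the investigational product.

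**Conclusion.** The point holds as a conflict between stated rules together with a gap. SAP 10.1 sets device-relatedness by event type (17 of 22 rows non-ADE, 3 in neither column, 2 skin reactions ADE). The ADE bullet in SAP section 10 covers only anticipated AS-101 events. Both conflict with the promised summary by relationship to Airmod, and nothing states which governs. Harm linked to a wrong or missing Airmod reading may therefore be labelled non-ADE and missed for endpoint 5 and for the device-related trigger in SAP 7.5.3.

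The size of any resulting bias in the safety conclusion cannot be calculated from the documents; its direction would be toward finding no device effect. The conclusion assumes that those who classify events would follow the table's labels, and that neither the AE form nor the DSMB charter, which were not supplied, contains an overriding causality rule. If either does, the remaining task is to bring the SAP text into line with it. The point should be corrected in the SAP, but it does not affect the efficacy analyses.

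**What to change.** Reconcile SAP section 10 and SAP 10.1 with Protocol 9.4.4:

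1. Keep the SAP 10.1 list as expected procedural events, and replace the ADE and non-ADE columns with expected / not expected.
2. State that the investigator judges relationship to Airmod and to AS-101 for every event, whatever its row, and give the causality criteria and an operational definition of USADE.
3. Reword the ADE bullet to cover all device-related events, anticipated and unanticipated, for Airmod as well as AS-101.
4. State that this per-event judgement determines endpoint 5 and what is reported to the DSMB as device-related.
5. If AirRR is to be checked against the reference around an apnea, desaturation or arrest, do so afterwards from the stored recordings. Under SAP 8.2.1, ManCRR is scored by researchers from the recorded trace and then verified by the principal investigator, so an AE form completed at onset could not show that AirRR was wrong.

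The cost of items 1 to 4 is SAP wording and, if the AE form lacks them, a relationship field for each of the two devices. Item 5, if adopted, adds a retrospective comparison for the selected events. The downside is that some events may be counted as device-related that the current table would not count. Sample size and efficacy analyses are unchanged.
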